
iron by comparing with elemental analysis, the gold standard. This *in vivo* patient project is designed to demonstrate that QSM will provide much better image quality and higher sensitivity than R2* quantitatively mapping iron in SNc.

STUDY DESIGN

Prospective, single center trial to determine whether the current R2* iron mapping method for measuring nigral iron changes in Parkinson's Disease (PD) can be significantly improved by using the Quantitative Susceptibility Mapping (QSM) based iron mapping techniques with the goal of validating QSM for potential use in later clinical trials. This study will include six cohorts - Parkinson's Disease (PD) Stage I (20 subjects), PD Stage II (20 subjects), PD Stage III (20 subjects), PD Stage IV (20 subjects), REM Sleep Behavior Disorder (RBD) (10 subjects), and healthy controls (10 subjects). Subjects who meet the inclusion and exclusion criteria and whom sign an informed consent form will be eligible for participation in this study and will undergo the following assessments regardless of cohort stratification. Screening and Baseline: Subjects will be seen in the Movement Disorder Clinic within the Department of Neurology at Weill Cornell Medicine, or at HSS, or at Cornell Ithaca (other recruiting sites) for an in-office visit which will include review of medical history, concomitant medication review, physical exam, urine pregnancy test (females of childbearing potential age) and completion of clinical surveys. This visit may be a standard of care, office visit, or may be an office visit performed for research purposes. If standard of care, in-office neurological assessments have already been performed within three months of study imaging, this may be used to satisfy the study baseline/screening and 24 month in office assessments. All subjects, whether recruited at WCM or HSS, will receive either a PE2i Positron Emission Tomography (PET) scan or DaT single photon emission computed tomography (SPECT) scan, and Magnetic Resonance Imaging (MRI) scan of the brain at WCM. If the subject received a standard of care MRI scan of the brain within 1 month of screening, this exam will be utilized to satisfy the baseline requirement for an MRI of the brain. However, if a standard of care MRI of the brain was performed either at an outside facility or at New York Presbyterian-Weill Cornell Medicine outside the required 1 month window to enrollment, the MRI of the brain will be repeated at Baseline as performed for research purposes. Month 24 (+/- 2 Months): Subjects will be seen in the Movement Disorder Clinic within the Department of Neurology at Weill Cornell Medicine, or at HSS for an in-office visit (either as a standard of care office visit, or may be an office visit for research purposes) which will include review of medical history, review concomitant medications, physical exam, urine pregnancy test (females of childbearing potential age), complete surveys; and subjects will receive a repeat PE2i PET scan or DaT scan and MRI of the brain at WCM. The following outlines which procedures are considered performed for research purposes vs. performed for standard of care purposes for PD and RBD Cohorts: Performed for Research Purposes: PE2i PET Scan or DaT scan performed at Baseline and Month 24 visit; MRI of the brain performed at Baseline (only if repeated for research purposes as outlined above) and Month 24 visit; Urine pregnancy test for female subjects of child-bearing potential age performed at baseline and Month 24 visit. Performed for Standard of Care Purposes: Office visit performed at Baseline and Month 24 visit (unless subjects are asked to return for an office visit performed for research purposes with the Neurology team at WCM or HSS); MRI of the brain performed at Baseline visit; Completion of clinical neurological surveys (e.g. UPDRS). Subjects recruited at Cornell Ithaca will have the MRI at the Cornell MRI Facility and may or may not have a PE2i PET scan or DaT scan at WCM. Subjects who receive the DaT scan will have to take Lugol's solution before scanning to protect their thyroid.

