
Our primary objective is to establish that Quantitative Susceptibility Mapping (QSM) is more sensitive than R2* for nigral iron mapping in monitoring PD iron overload.

Our secondary objective is to evaluate rate of iron accumulation throughout different disease stages.

1. Unified Parkinson's Disease Rating Scale (UPDRS) scores to monitor for clinical changes.
2. Quantitative PE2i PET scan estimations to monitor for dopaminergic degeneration.

INCLUSION AND EXCLUSION CRITERIA

Inclusion Criteria:

1. Idiopathic Parkinson's Disease, REM sleep behavior disorder subjects without signs of Parkinsonism and normal healthy controls.
 - a. If tremor is not present, subjects must have unilateral onset and persistent asymmetry of the symptoms.
 - b. For PD subjects only: age > 30 years at time of diagnosis of PD with a maximum age of 100 years old.
 - c. Hoehn & Yahr stage < V (if PD)
2. For PD subjects only: receiving an optimized dopaminergic regimen (i.e., either MAO-B inhibitor, a dopamine agonist and/or low doses of L-dopa, with dose change no more frequent than every 6-months in the course of the study); or medications naïve
3. No overt anemia, iron deficiency, or other hematological disorders
4. Deemed healthy and able to undergo MRI and PE2i PET imaging by the site investigator, based on screening assessments—medical history, physical examination
5. For controls and REM sleep behavior disorder subjects only: age 20-80; willing to undergo multiple imaging sessions
6. Signed informed consent form

Exclusion Criteria:

1. Patient with atypical parkinsonism (such as suspected Progressive Supranuclear Palsy, Multiple System Atrophy) and secondary parkinsonism (such as normal pressure hydrocephalus, drug-induced, or vascular parkinsonism)
2. Patients with uncertainty as to having classical Parkinson's disease, such as those who might have scans without evidence of dopaminergic deficits (SWEDDs)
3. Presence of a medical or psychiatric comorbidity that can compromise participation in the study
4. Patients with clinically significant depression as determined by the Beck depression score > 15
5. History of exposure to typical or atypical neuroleptics or any dopamine blocking agent within 6 months prior to enrollment
6. Patients with psychosis/active hallucinations and memory difficulty pre-dating the onset of motor symptoms

7. History of brain surgery for PD
8. Untreated thyroid disease
9. History of stroke or cerebral vascular disease
10. History of drug abuse

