Clinical outcome assessments: The six subject cohorts will be compared to assess differences in their clinical evaluations and MRI iron measurements obtained in this study. MRI iron measurements will be correlated with clinical evaluations to estimate iron overload effects at baseline visit and month 24 visit after enrollment. Also, these MRI iron measurements will be correlated with rate of dopaminergic loss if detected by PE2i PET or DaT scan imaging. Statistical analyses: All analyses will be performed using a statistical software (SPSS, Chicago, IL). The kappa test will be used to assess reader agreements, and covariance analysis (adjusted for baseline differences) to estimate clinical outcomes as measured by UPDRS at baseline and 24 Months, and PE2i PET or DaT scans at baseline and 24 Months. For non-normally distributed data, the robustness will be checked after log transformation. The analysis of variance assumption will be validated by residual analysis, and the size effect will be adjusted for baseline differences. Correlation and logistic regression will be performed among various MRI and PE2i PET or DaT scan measurements and other clinical data. The longitudinal data will be modeled using the generalized estimating equation (GEE) to assess significant change. Paired t-test and ROC curve comparison will be performed to assess differences between QSM and R2*.

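### Standard GEE would reject somewhat too often for iron change by PD stage (about 6–8% at an assumed 5%) because the SAP sets no small-sample rule for cohorts of 20

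*Combined protocol and SAP*

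**What the plan says.** The Statistical Analysis Plan section states: "The longitudinal data will be modeled using the generalized estimating equation (GEE) to assess significant change". It does not say which contrasts will be tested, which variance estimator or reference distribution will be used, or at what significance level.

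The secondary objective, stated just before the Inclusion and Exclusion Criteria, is to "evaluate rate of iron accumulation throughout different disease stages". Study Design plans 20 subjects in each of PD Stages I to IV and smaller numbers in the other two groups: "PD Stage IV (20 subjects), REM Sleep Behavior Disorder (RBD) (10 subjects), and healthy controls (10 subjects". Imaging is at two visits, baseline and month 24.

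Other methods are named in the same section:

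- Covariance analysis is assigned to UPDRS and to PE2i PET or DaT at both visits.
- Analysis of variance appears without an outcome: "The analysis of variance assumption will be validated by residual analysis".
- The cohort comparison has no method attached: "The six subject cohorts will be compared to assess differences in their clinical evaluations and MRI iron measurements obtained in this study".
- QSM and R2* are compared by paired t-test and ROC curves.

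GEE is therefore not the only analysis of two-visit data, but it is the only one clearly linked to change in MRI iron.

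**The concern.** The usual GEE test divides the estimated change by a sandwich standard error and refers the ratio to the normal distribution (chi-square for joint tests). It relies on a large number of independent subjects. For change within a stage, the relevant number is the 20 in that stage and not the 100 in the study. At that size the sandwich variance is biased downward, and the normal reference ignores the uncertainty in the variance.

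At stake is the secondary objective. Confidence intervals for iron accumulation in each stage would be too narrow, and differences in rate between stages would be declared more often than the nominal level allows.

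**Working it through.** The plan has no sample-size calculation, power figure or significance level, so there is no figure to reproduce.

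**Inputs from the documents.** n = 20 per PD stage, n = 10 for RBD and for controls, 100 in total, two visits.

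**Assumptions.** Two-sided 5% (critical value 1.96), complete and normally distributed changes, and the uncorrected sandwich variance with a normal or chi-square reference.

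**Change within one cohort (exact).** With two visits the GEE estimate is the mean change. Its sandwich variance is the sum of squared deviations divided by n², where the unbiased form uses n(n − 1). The test therefore rejects when |t| > 1.96 × √((n − 1)/n), with t on n − 1 degrees of freedom.

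- n = 20: 1.96 × √(19/20) = 1.910; P(|t₁₉| > 1.910) = 7.1%.
- n = 10: 1.96 × √(9/10) = 1.859; P(|t₉| > 1.859) = 9.6%.
- n = 100 (pooled change): P(|t₉₉| > 1.950) = 5.4%.

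GEE models fitted to simulated data (exchangeable working correlation, robust variance, 4,000 runs each) gave 7.1% at n = 20 and 9.3% at n = 10, in line with the formula.

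**Two stages of 20.** The same cut-off with 38 degrees of freedom: P(|t₃₈| > 1.910) = 6.4%.

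**Tests across cohorts (simulated under no difference, 200,000 runs for the joint tests).**

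| Test | Uncorrected GEE | Bias-corrected sandwich (Mancl-DeRouen) with F | Welch F on change | ANOVA on change, equal variances |
|---|---|---|---|---|
| Linear trend, Stages I–IV | 6.2% | – | – | – |
| Four stages of 20 | about 8% | 5.2% | 5.0% | 4.9% |
| All six cohorts | about 12% | 6.6% | 5.3% | 5.0% |

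**Interval width.** Within a stage of 20 the correct multiplier is t(0.975, 19) = 2.093. The ratio 1.910/2.093 = 0.913, so the uncorrected interval is about 9% too narrow. Equivalently, the corrected interval is 2.093/1.910 = 1.096 times as wide, about 10% wider. For 20 v 20, 2.024/1.910 = 1.060, about 6% wider.

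**Power.** For 20 v 20 at an assumed difference in change of 0.9 SD, nominal power is 82% with uncorrected GEE and 79% with Welch. For the four-stage test with evenly spaced stage means spanning an assumed 1 SD, it is 83% and 77%. Part of the higher GEE figures is the inflated error rate.

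**The case against.** **This is an omission and not a stated wrong choice.** The team could use a corrected GEE, or an ordinary analysis of variance on change, which holds its level under equal variances. That is true, and every figure above is conditional on the standard version. But the plan leaves the choice open, and the standard version of the method it names has the problem.

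**The effect is small.** This also stands. The objective concerns PD stages, and for those the excess over 5% is between about 1 and 3 percentage points.

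**Stronger readings that a reader might infer.**

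- *That the plan's error rate is 10–12%.* Those figures need GEE to be applied to the 10-subject RBD and control cohorts. The SAP compares six cohorts but does not assign that comparison to GEE.
- *That a stated error rate is exceeded.* No error rate is stated; 5% is an assumption here.
- *That all two-visit analyses are affected.* Covariance analysis is named for UPDRS and for PET or DaT, so the point is confined to MRI iron.
- *That the primary objective is undermined.* The comparison of QSM with R2* is planned by paired t-test and ROC curves, not GEE.

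**Conclusion.** The concern holds as a minor, conditional point on the secondary objective. If standard GEE is used for change in MRI iron by PD stage, the true type I error lies between about 6% (trend or two stages) and 8% (four-stage test), and is 7.1% within a stage. Within-stage intervals are about 9% too narrow. The error is larger, 9.6% within a cohort and about 12% for a six-cohort joint test, only if GEE is also used for the 10-subject groups, which the plan does not specify. Pooled change over 100 subjects is close to nominal. These results rest on an assumed two-sided 5%, normal changes and no missing second visits. A method that holds its level is available at almost no cost, so the change is worth making.

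**What to change.** Add to the Statistical Analysis Plan:

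> Change in QSM and R2* within each cohort, and differences in change between cohorts, will be tested at two-sided 5% using one-sample t tests and Welch t/F tests on the 24-month change. If GEE is used, it will use a bias-corrected sandwich variance with t/F reference distributions.

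For the four PD stages, the corrected GEE with an F reference is essentially nominal (5.2%). Some excess remains (6.6%) if the 10-subject cohorts are included.

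A mixed model with small-sample degrees of freedom is an acceptable alternative if covariates are wanted. Age is a plausible one, because its limits differ by group: "age > 30 years at time of diagnosis of PD with a maximum age of 100 years old" for PD, against "For controls and REM sleep behavior disorder subjects only: age 20-80". The plan says "All analyses will be performed using a statistical software (SPSS, Chicago, IL", so the team should first confirm that its SPSS version supports the chosen option.

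The cost is SAP wording only, with no added subjects, visits or data. Compared with uncorrected GEE, intervals are about 6% (20 v 20) to 10% (within 20) wider, and nominal power falls by the few points shown above.

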To help the development of iron chelation as a potential therapy for Parkinson's Disease (PD), this study is designed to establish an accurate and sensitive Quantitative Susceptibility Mapping (QSM)-based Substantia Nigra (SN) iron mapping method. Furthermore, should trials of iron chelation therapy in PD prove that this intervention has clinical effectiveness, an improved method to measure SN iron concentration (such as QSM as proposed herein) could become a companion Radiological Biomarker for triage and response assessment; and potentially for dose modulation to prevent potential over-treatment. We propose a study to assess SN iron changes to test the hypothesis that the QSM based iron mapping technique is more sensitive than the current $R2^*$ method for monitoring nigral iron change in PD patients. Prooxidant iron accumulation in the substantia nigra pars compacta (SNc) in the midbrain is one possible reason for SNc vulnerable to neurodegeneration. Increased iron in SN of PD patients have been evaluated by various MRI methods to be correlated with disease severity, duration, and other patient assessments. Longitudinal studies show that iron estimated by MRI progressively increase in PD subjects but not in controls. Iron elevation can cause cell death mediated by oxidative stress. The increased iron is located within individual dopaminergic neurons in the PD SNc, which leads to the following consequences: 1) The interaction of ferrous iron (Fe(II)) with oxygen (hydrogen peroxide) readily generates highly toxic hydroxyl radicals ($HO\cdot$) via Fenton chemistry. Post mortem PD-affected brains display increased lipid peroxidation, oxidative damage to DNA, and lowered levels of the reduced form of glutathione, which all reflect oxidative stress. 2) Iron can impact the aggregation of alfa-synuclein, the major component of Lewy bodies in PD. Alfa-synuclein binds to iron, which accelerates its aggregation into fibrils and is consistent with pathological finding of enriched iron in Lewy bodies. Alfa-synuclein has also been shown to directly generate hydrogen peroxide when it aggregates and, in the presence of iron, produces toxic hydroxyl radicals. 3) The aggregation of alfa-synuclein in PD can proliferate microglia, and iron can polarize microglia to the pro-inflammatory M1 phenotype that produces cytotoxic cytokines, which is observed in the advanced dopaminergic degeneration in symptomatic PD. While noninvasive MRI is sensitive to the presence of iron that is paramagnetic, current MRI methods to quantify iron are highly problematic. A commonly used method is the signal decay rate $R2^*$, to be precise, the decay rate of the magnitude signal along the data sampling echo time TE in the commonly used gradient echo sequence. We have found that $R2^*$ suffers from various problems including 1) dependences on imaging parameters including voxel size and field strength, 2) blooming artifacts, which are particularly strong at SNc that is near the nasal cavity air-tissue interface of strong magnetic susceptibility difference, and 3) interfering effects from cellular contents such as membranes, proteins (neuromelanin, alpha-synuclein, etc). Our investigations have lead to the physics insight to model MRI signal dependence on paramagnetic iron, which is the so called forward problem from iron to MRI signal phase or field. Accordingly, we have innovated the inverse solution from field to iron source, which is termed as quantitative susceptibility mapping (QSM). We are performing ex vivo studies to demonstrate that QSM is much more accurate than $R2^*$ for measuring

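### The only planned QSM-versus-R2* comparison leaves the paired t-test's input and the ROC's reference and visit unstated, and a t-test on unstandardised values or changes would not test sensitivity

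*Combined protocol and SAP*

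**What the plan says.** The objectives text of the combined protocol and SAP sets the primary aim, to "establish that Quantitative Susceptibility Mapping (QSM) is more sensitive than R2* for nigral iron mapping in monitoring PD iron overload". The background puts the hypothesis in terms of change: QSM is more sensitive than the current R2* "method for monitoring nigral iron change in PD patients". Just before STUDY DESIGN it adds image quality, claiming that "QSM will provide much better image quality and higher sensitivity than R2* quantitatively mapping iron in SNc".

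The background also says what each map measures. R2* is "the decay rate of the magnitude signal along the data sampling echo time TE". QSM is "the inverse solution from field to iron source, which is termed as quantitative susceptibility mapping (QSM"). Among the problems it lists for R2* are "interfering effects from cellular contents such as membranes, proteins".

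In STATISTICAL ANALYSIS PLAN, only the closing sentence sets one map against the other: "Paired t-test and ROC curve comparison will be performed to assess differences between QSM and R2". The rest of that section covers cohort comparisons, correlations of MRI iron measurements with clinical scores and dopaminergic loss, covariance analysis of UPDRS and PET/DaT, logistic regression, GEE for longitudinal change, and reader agreement ("The kappa test will be used to assess reader agreements"). None of these is stated as a contrast between QSM and R2*. The documents give no alpha, SD, effect size, power or success criterion for the primary objective.

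**The concern.** Two methods are named, but neither can be run from the text. For the t-test, the paired quantity could be the value at one visit, the 24-month change, a standardised change or a reader score. For the ROC, the plan has six cohorts and two visits and ties none of them to the curve.

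The t-test has a further problem that filling in details does not always cure. The background describes a decay rate and a susceptibility, and no calibration to a common scale is given. Subtracting one from the other yields a difference whose sign depends on the units chosen.

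At stake is the study's main claim, which STUDY DESIGN says is meant to validate QSM for later trials. If the input, reference and visit are chosen after the data are seen, the result can depend on that choice.

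**Working it through.** There is no sample-size or power figure in the plan to reproduce. The cohort counts are 4 × 20 PD, 10 RBD and 10 controls (100 in all). Every SD, effect, correlation, AUC and alpha below is an assumption.

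**1. Definition.** SRM (standardised response mean) = mean 24-month change / pooled within-stage SD of change. The t-test illustrations assume the same mean change in every stage, so this is simply the SD of change.

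**2. Paired t-test in native units.** With means m, SDs s, correlation r and n subjects,

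t = √n × (mQ − mR) / √(sQ² + sR² − 2·r·sQ·sR).

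Assume n = 80, r = 0.5, change SD 10 ppb (0.010 ppm) for QSM and 2 per second for R2*. At equal SRM 0.5 the means are 5 ppb and 1 per second.

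- ppb: 8.944 × (5 − 1) / √(100 + 4 − 20) = 8.944 × 4 / 9.165 = **+3.90**.
- ppm: 8.944 × (0.005 − 1) / √(0.0001 + 4 − 0.02) = 8.944 × (−0.995) / 1.995 = **−4.46**.

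| SRM, QSM / R2* | t, QSM in ppb | t, QSM in ppm | t, each change divided by its own SD |
|---|---|---|---|
| 0.5 / 0.5 | +3.90 | −4.46 | 0.00 |
| 0.8 / 0.4 | +7.03 | −3.55 | +3.58 |
| 0.4 / 0.8 | +2.34 | −7.16 | −3.58 |

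The unit alone sets the sign in the two middle columns. Only the last column follows sensitivity. In simulation (20,000 trials per cell, r from 0.3 to 0.9, n = 80 or 60) with equal SRM 0.5, the test favoured QSM in 89–99% of trials in ppb, R2* in 97–99% in ppm, and QSM in 3.5–4.1% when each change was divided by its own SD.

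**3. Paired t-test on a common iron scale.** The unit problem goes, but the numerator is still a difference in means.

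- Same mean change, QSM twice as sensitive (SRM 1.0 vs 0.5): mQ − mR = 0, so the expected t is 0. Simulation favoured QSM in 2–3%, against 86–100% when standardised.
- Equal SRM 0.5, R2* reading 30% low: with mean change 1, sQ = 2 and sR = 1.4, t = 8.944 × 0.3 / √(4 + 1.96 − 2.8) = 1.51. Simulation over the full range favoured QSM in 19–79%, although the maps are equally sensitive.

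**4. ROC.** AUC does not change when a marker is rescaled, so step 2 does not apply to it. The reference still matters. Take AUC 0.85 vs 0.75, two-sided 0.05, correlation between AUC estimates 0.3–0.7. For PD vs controls the Hanley-McNeil SEs are 0.050 and 0.070. At correlation 0.5 the SE of the difference is 0.062, and power is Φ(0.10/0.062 − 1.96) = 36%.

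| Reference | Power |
|---|---|
| 80 PD vs 10 controls | 28–52% |
| 80 PD vs 20 controls and RBD | 42–73% |
| 40 stage III–IV vs 40 stage I–II | 40–72% |
| 20 stage I vs 10 controls | 18–34% |
| 10 RBD vs 10 controls | 13–24% |

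The visit matters too. On 24-month change, with no mean change in controls, SRM 0.75 vs 0.50 corresponds to AUC Φ(0.75/√2) = 0.70 vs Φ(0.50/√2) = 0.64. Simulated power with 80 PD and 10 controls was 10–16%.

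**5. A unit-free alternative.** The difference in SRM was given a 95% interval by resampling subjects, both maps together, within stage. At equal SRM 0.5 the lower limit exceeded 0 in about 3–4% of trials. Power for 0.75 vs 0.50 at correlation 0.5 was roughly 40–55% across runs with 80 or 60 PD subjects. The weakness is non-iron change: a 0.25 SD drift in R2* turns 0.50 into 0.75, the two SRMs become equal, and claims for QSM fall from 52% to 2.7% (n = 80).

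**The case against.** A reader might infer that the primary objective has no test at all. That goes too far: the SAP names two methods for QSM against R2*. The ROC is unit-free and relevant to discrimination, and PD versus healthy controls is an obvious candidate reference, though unstated.

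A reader might also infer that the plan subtracts raw R2* from raw QSM. The documents do not say this and state no measurement units. Reader scores are a supportable reading, since image quality is claimed and kappa for readers is planned, and a paired t-test of such scores would be acceptable. But that serves a different aim and would leave only the unspecified ROC for sensitivity. A common iron scale is also conceivable because both maps are called iron measurements. No calibration is described, and step 3 shows that calibration would not make the t-test a test of sensitivity.

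The strongest point against the remedy stands. The SRM counts any consistent change, including the non-iron R2* effects the background names, so as a decision rule it can point the wrong way. It is therefore offered as one example, reported with its interval. It is also fair that the study is observational with no therapeutic intent. That limits the harm, but a stated validation goal still needs a stated comparison.

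**Conclusion.** The concern holds in this form: the primary comparison is named but underspecified, and the paired t-test is not a valid test of sensitivity if applied to unstandardised QSM and R2* values or changes. Both follow from the SAP text and the t formula, without any assumed value.

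The size can only be illustrated. With assumed SDs and equal sensitivity, changing ppb to ppm moves t from +3.90 to −4.46, and on a common scale a twofold QSM advantage with equal mean change is found in 2–3% of trials. A reader might take these as error rates of this trial. They are not: the documents give no SDs, effects, correlations or dropout, and the t-test's actual input is unknown. The reversal by units applies to the t-test only. What can shift the ROC result is the choice of reference and visit.

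**What to change.** 1. State the t-test's input. If it is for reader image-quality scores, say so and keep it for that aim. Do not use it on unstandardised QSM and R2* values or changes to support the primary objective.
2. Name one unit-free paired comparison of sensitivity to change and state in advance how its interval will be read. Example wording: *In PD subjects with MRI at both visits, using the same nigral region on both maps, SRM is the mean 24-month change divided by the pooled within-stage SD of change. SRM(QSM) minus SRM(R2\*) is reported with a 95% bootstrap interval that resamples subjects, both maps together, within baseline stage.*
3. Keep the ROC as a paired AUC difference with a stated reference and visit, for example baseline PD versus healthy controls. Label it cross-sectional discrimination and report its interval, because there are only 10 controls.
4. Describe the SRM difference as responsiveness, not proof of iron sensitivity. Report beside it the already planned correlations with PET or DaT loss, using each map's change and computed within tracer. Their difference will be imprecise: with both correlations at 0.3 (assumed), the 95% half-width is 0.16–0.25 with 80 subjects and 0.23–0.35 with 40. STUDY DESIGN also allows Ithaca subjects to have no such scan.

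The cost is SAP wording, a short script and one added line in the software statement, since the bootstrap probably lies outside the standard SPSS menus. No new scans, visits or subjects are needed. The downsides are modest power and no separation of iron from non-iron change. The SRM denominator also includes true variation between patients.
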